6.0 RISKS AND BENEFITS

PET:

Detailed organ dosimetry derived from four representative patients is included in the table below. Of note, the effective dose from ^{18}F -DCFPyL was 0.0165 mSv/MBq or 6.1 mGy (0.61 rem) for an injected dose of 370 MBq (10 mCi), or 5.49 mGy or 5.49 mSv (0.549 rem) for 333 MBq (9 mCi) which is the highest dose administered for each scan in this study.

Dosimetry:

Highest radiation dose was estimated for the kidneys (0.0945 mGy/MBq) followed by urinary bladder wall (0.0864 mGy/MBq), submandibular glands (0.0387 mGy/MBq) and liver (0.0380 mGy/MBq). The mean absorbed dose to the bone marrow was 0.01 mGy/MBq. In comparison to the published data on our first generation agent, ^{18}F -DCFBC, ^{18}F -DCFPyL shows significantly lower (under 50 %) doses in most radiosensitive organs such as the thymus, ovaries, red marrow and osteogenic cells. Less radiation dose was also measured in lower large intestinal wall, small intestine, stomach wall, lungs, muscle and skin. Radiation dose from the two radiotracers was similar (within +/-50 %) in the gallbladder wall, upper large intestinal wall, spleen, testicles, thyroid, and pancreas. Radiation dose from ^{18}F -DCFPyL was higher in the adrenals, kidneys, liver, pancreas, spleen, and bladder wall.

Organ	Absorbed Dose (mGy/MBq)
Adrenals	3.11E-02
Brain	2.19E-03
Breasts	4.57E-03
Gallbladder Wall	1.44E-02
Heart Wall	1.29E-02
Kidneys	9.45E-02
Lacrimal Glands	3.50E-02
Lens	1.25E-03
Liver	3.80E-02
LLI Wall	1.05E-02
Lungs	1.08E-02
Muscle	6.32E-03
Osteogenic Cells	9.58E-03
Urinary Bladder Wall	8.64E-02

Organ	Absorbed Dose (mGy/MBq)
Ovaries	8.89E-03
Pancreas	2.44E-02
Parotid Glands	2.68E-02
Red Marrow	1.04E-02
Skin	4.05E-03
Small Intestine	9.13E-03
Spleen	1.85E-02
Stomach Wall	1.16E-02
Submandibular Glands	3.87E-02
Testes	1.01E-02
Thymus	5.56E-03
Thyroid	8.56E-03
ULI Wall	1.67E-02
Uterus	1.15E-02

CT:

Risks associated with CT include exposure to 10.0 mSv of radiation from the low-dose scan required for attenuation correction calculations. Thus, the total whole body effective dose equivalent for a PSMA PET/CT is approximately 15.5 mSv (5.5 mSv from PSMA-PET plus 1.0 mSv from CT). This corresponds to approximately 4 years of natural background radiation. The total whole body effective dose equivalent for 2 and 3 PSMA PET/CT scans performed over a one year time period is 31.0 mSv and 46.5 mSv, respectively, and remain below the annual occupational dose limit for radiation workers (50 mSv) in a one year time period. If a patient receives a 4th or 5th PSMA PET/CT scan during a one year time period due to inclusion of PET3A and 3B timepoints for PET/CT imaging at time of 2nd systemic therapy, the

total whole body effective dose equivalent will be 62 mSv and 77.5 mSv, respectively. The PET4 timepoint PSMA PET/CT will be performed at the time of tumor recurrence or two years after initiation of therapy (whichever one comes first). (Median OS for metastatic RCC patients is approximately 24 months.)

7.0 ADVERSE EVENTS AND SAFETY ISSUES

Definition of adverse events and potential risks: The term “adverse event” is defined in the International Conference on Harmonization Guideline for Good Clinical Practice as follows: “Any untoward medical occurrence in a patient or clinical investigation subject administered a pharmaceutical product and which does not necessarily have a causal relationship with this treatment. An adverse event (AE) can therefore be any unfavorable and unintended sign (including an abnormal laboratory finding), symptom, or disease temporally associated with the use of a medicinal (investigational) product whether or not related to the medicinal (investigational) product”.

Medical conditions of a subject that exist prior to receiving the investigational imaging tracer will be recorded as medical history. After administration of the investigational imaging tracer, all new medical conditions are considered adverse events. Adverse events occurring in this trial will be recorded in data collection forms, regardless of whether or not they are thought to be associated with the investigational imaging tracer throughout the study period. However, the Investigator also will assess the possible relationship between the adverse event and the investigational imaging tracer.

For the purposes of this protocol, an adverse event (AE) is any untoward medical occurrence (e.g., sign, symptom, disease, syndrome, intercurrent illness, abnormal laboratory finding) that emerges or worsens relative to pre-imaging baseline. We anticipate minimal adverse effects or toxicity with the investigational imaging tracer ¹⁸F-DCFPyL in this study.

Definition of Serious Adverse Events (SAE), SAE list: Any adverse drug experience, occurring at any dose that results in any of the following:

- Death
- Is life-threatening (an event in which the patient was at immediate risk of death; it does not refer to an event which hypothetically might have caused death if it were more severe)
- Requires or prolongs inpatient hospitalization
- Results in a persistent or significant disability/incapacity
- Is a congenital anomaly/birth defect
- Important medical events that may not result in death, be life-threatening, or require hospitalization may be considered serious when, based upon appropriate medical judgment, they may jeopardize the patient or subject and/or may require intervention to prevent one of the outcomes listed.

All other AEs will be treated as “non-serious” and are described in the final study report. An SAE that is definitely, probably or possibly related to the investigational imaging tracer will be reported immediately (within 24 hours of its determination) by telephone or fax by the Principal Investigator.

AE Characteristics: Toxicity will be graded according to the NCI Common Toxicity Criteria (CTCAE), version 4.03 (Appendix A; which can also be accessed and downloaded via the website: <http://ctep.cancer.gov/reporting/ctc.html>). The Investigators will monitor the occurrence of adverse events during the course of each patient in the study. The Investigators need to assess whether there is a reasonable possibility that the study imaging agent caused or contributed to an AE using the following criteria as a guide:

- Definite: The adverse event is clearly related to the investigational agent.
- Probable: There is a clinically plausible time sequence between the onset of the AE and administration of imaging tracer. The AE is unlikely to be caused by the concurrent/underlying illness, other drugs, or procedures.
- Possible: There is a clinically plausible time sequence between the onset of the AE and administration of imaging tracer, but the AE could also be attributed to the concurrent/underlying disease, other drugs, or procedures. “Possibly” should be used when the administration of the study imaging tracer is one of several biologically plausible causes of the AE.
- Unlikely: The adverse event is doubtfully related to the investigational imaging tracer.
- Not Related: Another cause of the AE is the most plausible and/or a clinically plausible temporal sequence is inconsistent with the onset of the AE and the investigational imaging tracer; and/or a causal relationship is considered biologically implausible.

If any adverse event is considered to be definitely, possibly or probably related to the investigational imaging tracer, that event will be followed until resolution or until it is deemed chronic or irreversible by the Investigator. If an event is unlikely or not related to the investigational imaging tracer, the event will not be reported.

All AE will be documented and recorded in the medical record and will include:

- I. Specific reaction according to NCI Common Toxicity Criteria, version 4.0.
- II. Duration of the reaction
- III. Severity/grade according to NCI Common Toxicity Criteria, version 4.03. If the adverse event is not addressed by the Common Toxicity Criteria, the severity should be rated as mild (grade 1), moderate (grade 2), severe (grade 3), or life threatening (grade 4).
- IV. Relation of reaction to study agent
- V. Management of reaction, including any interruption or dose modification of the study drugs.

Event Severity: In addition to classifying an adverse event as serious or non-serious, the Investigator and/or designated personnel will grade the adverse event to describe The Maximum intensity of the event. Specific criteria for the intensity of adverse events are described in the Common Toxicity Criteria (CTC: National Cancer Institute). Investigators should follow these criteria for grading and reporting adverse events.

An event may be severe, but may not be serious (e.g., severe headache). The severity of an adverse event will be assessed by study personnel using their best clinical judgment and includes but is not limited to taking into account the patient's past history, the patient's chart, interviews with the patient and

caregivers, and direct observation. The Investigator will also be asked to assess the possible relationship between the adverse event and the administration of the investigational imaging tracer.

Adverse Event Reporting: Per 21CFR312.32(c), all adverse events deemed both serious and unexpected associated with the use of the drug must be reported to the FDA and to all participating investigators as soon as possible and in no event later than 15 days.

The FDA will be notified of any unexpected fatal or life threatening experience associated with the drug as soon as possible but in no event later than 7 calendar days. The UW HS-IRB will be notified in accordance with posted institutional policy.

Adverse Events: Serious and Non Serious Adverse events will be recorded, regardless of whether or not they are thought to be related to the investigational imaging tracer. While all adverse events will be tabulated and reported in the study final report, serious adverse events will be reported in the course of the trial. Adverse events that meet criteria of a serious adverse event listed above will also be recorded and reported.

The Investigator will inform the IRB of all adverse events attributed to the investigational imaging tracer in accordance with posted institutional policy.

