¹⁸F-DCFPyL PSMA-dependent uptake within PSMA positive PC3 PIP xenografts, reaching a value of 46.7 ± 5.8%ID/g at 30 minutes post-injection (p.i.), which decreased by only about 10% over the ensuing 4 hours. At 60 minutes p.i. the kidney, liver, and spleen displayed the highest uptake. By that time, the urinary bladder also showed relatively high uptake. However, that uptake includes excretion at all-time points. Rapid clearance from the kidneys was shown, decreasing from 74.1 ± 6.6%ID/g at 30 minutes to 7.4 ± 0.9%ID/g at 4 hours. The relatively high values noted in kidney are partially due to high expression of PSMA within proximal renal tubules. The ratio of uptake within PSMA positive PIP to PSMA negative flu tumors ranged from 40:1 to more than 1,000:1 over the 4-hour time period of the study. A possible explanation for that increased tumor uptake of radiochemical over time could be due to ligand-mediated PSMA internalization within tumor cells. Less retention in

kidney relative to tumor over time could be due to a lower degree of internalization in this (normal) tissue and/or different metabolism of ¹⁸F-DCFPyL, which does not promote retention of radiochemical in kidney. Relatively low bone uptake (<1% ID/g at all-time points) suggests little metabolic defluorination of ¹⁸F-DCFPyL. The total effective dose for 333 MBq (9 mCi) of ¹⁸F-DCFPyL was calculated to be 5.93 mGy (0.593 rem) based on animal models.

Initial Phase I Study Adverse Events:

An initial phase I study of the biodistribution and dosimetry of ¹⁸F-DCFPyL found that in nine patients there were no severe adverse events. One patient reported two adverse events that were classified as unlikely to be attributable to the radiotracer (mild headache and mild nose bleed, both of which resolved without treatment and were considered Grade I by the National Cancer Institute Common Terminology Criteria for Adverse Events (NCI CTCAE) Version 4.0). Another participant experienced a decrease in platelet count on routine assessment during the post-imaging follow up which, at the time of publication, had not resolved but which was attributed to the participant starting treatment for prostate cancer. This was also a NCI CTCAE Grade I adverse event. There were no radiotracer-related adverse events with monitored heart rate or blood pressure.

Human dosimetry: ¹⁸F-DCFPyL human dosimetry reported in Risks/Benefits section.

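### Section 7.0 contradicts itself on whether adverse events judged unlikely or not related to the tracer are reported

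*Combined protocol and SAP*

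**What the plan says.** All the reporting rules are in Section 7.0.

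- **Exclusion by attribution.** After the five-level relatedness scale and the follow-up rule for related events, the text reads: "If an event is unlikely or not related to the investigational imaging tracer, the event will not be reported".
- **Final report, non-serious events.** Just before that scale, events that are not serious are classed as such "and are described in the final study report".
- **Final report and in-trial reporting.** The later paragraph on serious and non-serious events reads: "While all adverse events will be tabulated and reported in the study final report". The rest of that sentence has SAEs reported while the trial is running, with no relatedness limit. The paragraph adds: "Adverse events that meet criteria of a serious adverse event listed above will also be recorded and reported".
- **Reports limited by relatedness.** The 24-hour rule reads: "An SAE that is definitely, probably or possibly related to the investigational imaging tracer will be reported immediately". The notice to the IRB covers events attributed to the tracer, and the 15-day and 7-day FDA reports cover events associated with the drug.
- **Recording.** Events go on the data collection forms "regardless of whether or not they are thought to be associated with the investigational imaging tracer throughout the study period". The section also requires every event, with its relation to the agent, to be documented in the medical record.

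Section 9.0 adds external oversight. A committee meets annually to discuss adverse event and SAE reports and other data reports compiled by the study team. It meets ad hoc when an event occurs, to consider among other things whether the event is attributable to the research.

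**The concern.** One sentence removes a class of events from reporting on the strength of the investigator's attribution. Others in the same section put that class into the final report and, if serious, into reporting during the trial. Neither set refers to the other, so staff have no stated order of precedence.

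The class is unlikely to be small. Section 7.0 treats every new medical condition after tracer administration as an adverse event. The subjects have nephrectomy and then systemic cancer treatment, and the last scan may come two years after that treatment starts. Many events will have a plausible cause other than the tracer. The study is a single open-label cohort, so there is no control group against which a mistaken attribution would show.

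Three outputs depend on which rule is followed: the safety table in the final report, what happens in-trial to an SAE judged unrelated, and the list of events from which the Section 9.0 committee works.

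**Working it through.** The documents state no figure on this point, so there is none to reproduce. The check is a comparison of texts, report by report.

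| Report | Relatedness limit in its own rule | Compatible with the exclusion sentence? |
|---|---|---|
| 24-hour SAE report | Yes, definite, probable or possible | Yes |
| FDA 15-day and 7-day reports | Yes, associated with the drug | Yes |
| IRB notice | Yes, attributed to the tracer | Yes |
| SAEs reported during the trial | None | No, for SAEs judged unlikely or not related |
| Final report, non-serious events | None | No |
| Final report, all events | None | No |
| External committee (Section 9.0) | None | Not if the exclusion is applied to what the study team compiles |
| Data collection forms and medical record | None, all events recorded | Yes; this is recording, not reporting |

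The conflict is therefore confined to the final report, in-trial SAE reporting and, by consequence, the committee's list. Recording is consistent throughout.

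**Illustration.** Inputs are from the phase I account in Section 11.0.

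1. Patients: 9.
2. First patient with events: "One patient reported two adverse events that were classified as unlikely to be attributable to the radiotracer". That is 2 events.
3. Second patient with events: a fall in platelet count, put down to starting treatment for prostate cancer. That is 1 event.
4. Total: 2 + 1 = 3 events in 2 patients, none attributed to the tracer.
5. Mapping (assumption): the platelet event falls under unlikely or not related on this protocol's scale. The scale's definition of not related covers events for which another cause is the most plausible, which supports this.
6. Exclusion sentence applied: 3 − 3 = 0 events reported, in 0/9 patients (0%). The exact two-sided 95% interval is 0 to 1 − 0.025^(1/9) = 33.6%.
7. All-events rule applied: 3 events reported, in 2/9 patients = 22.2%, exact (Clopper-Pearson) 95% interval 2.8% to 60.0%.

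The same patients and events give either an empty table or one with 2 of 9 patients affected. The difference comes wholly from the reporting rule.

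**The case against.** The best defence is that the sentence means only expedited and IRB reporting. It closes a paragraph on attribution and follow-up, and the 24-hour and IRB rules are indeed limited to related events. The final report is dealt with expressly elsewhere, twice, and a specific rule would normally prevail over a general one. This is a reasonable guess at the intention, but the sentence does not say it. It would also leave open the SAE judged unrelated, which the later paragraph reports during the trial without any limit.

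Section 9.0 is a real safeguard. Attribution is not left to the investigators alone: the external committee considers it, and monitors verify that reported data are accurate and complete against source documents. That stands as mitigation. It protects less well if events are withheld before they reach the committee, since these would be the very events whose attribution it should examine.

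A reader might infer that unrelated events are lost, or that the tracer's safety summary will be biased toward zero. The documents do not support either. Section 7.0 requires every event to be recorded with its relation to the agent, so a full table can be rebuilt from the forms. Under-reporting follows only if staff apply the exclusion sentence over the explicit final-report rule. Nor does the recording requirement itself conflict with the exclusion sentence, because recording and reporting are different duties.

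**Conclusion.** The contradiction is literal and stands: as written, Section 7.0 both excludes and includes events judged unlikely or not related. It affects the reported safety table, in-trial reporting of unrelated SAEs, and possibly the committee's event list. It does not affect data capture, the sample size or the primary endpoint, and safety is not among the stated objectives.

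The size for this trial cannot be computed, because the documents do not forecast how many events will be judged unlikely or not related. The contrast of 0/9 with 2/9 comes from a different study, involves only two patients with events, and rests on the mapping assumed for the platelet event. It shows how the rules differ and should not be read as a forecast for these 15 subjects. The correction is worth making because the agent is investigational and the change is cheap.

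**What to change.** Replace the exclusion sentence and align it with the later paragraph on serious and non-serious events. The new text should do three things:

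1. Limit the exclusion to the reports already restricted to related events: the 24-hour SAE report and the IRB notice of attributed events.
2. State that all events, whatever their attribution, go to the monitoring committee and are tabulated by grade and attribution in the final report.
3. Say explicitly whether SAEs judged unlikely or not related are reported during the trial, as the later paragraph now states, and to whom.

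Possible wording for the first two: *Events judged unlikely or not related to the tracer are exempt from the 24-hour SAE report and from the IRB notice of attributed events. They are still recorded, provided to the monitoring committee, and tabulated by grade and attribution in the final report.* The third needs a further sentence once the sponsor-investigator has settled it.

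The cost is two or three sentences and slightly longer adverse event tables. No new data are collected.

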8.0 PRIVACY AND CONFIDENTIALITY PROTECTIONS

Research procedures will be conducted in private areas and we are only collecting the minimum amount of information necessary to conduct the study. No sensitive data (HIV status, illicit drug use) will be collected. Identifiable records will only be available to study team members.

Data are not being shared outside of UW except through publications, in which case the data do not identify individual subjects. Study data will be managed by the PI and co-PIs. Data will not be placed on unencrypted laptop computers. Coded electronic data will be kept on the secure network drives. A separate file linking codes to subject identity will be kept in the same manner, in a folder separate from study data. At the end of 7 years study data will be de-identified by destroying the link to identifiable information. Until that time data will remain coded and the file linking codes to subject identity kept as well.

All samples and images will be given a unique study number that cannot be linked to the patients' medical records in any way. Imaging research images will be stored on PACS under this study number only. The investigators will have access to the patients' electronic medical records that are relevant to this study. Study records will be kept for seven years. Study data will be managed by the PI and co-PI.

Subject's identifiable information will be linked to a study code. The study code will be used to identify the subject and research images. Research images may be used in scientific presentations, but all images will be de-identified. The data will be stored on the Principal Investigator's (PI or co-PI) password protected computer in her locked office. The code will be stored separate from the data on the PI's computer in her locked office.

9.0 DATA AND SAFETY MONITORING

Safety monitoring of research protocols investigating novel PET tracers utilize a combination of tools. These are framed to provide adequate clinical trial oversight ensuring that the research team is complying with the conditions of IRB approval and FDA requirements. The tools enable frequent evaluations of study-related activities, identification of deviations or noncompliance with the conduct of the study or protocol, review of adverse events tracking and reporting, and review of drug production and accountability.

These tools include:

- Study visit checklists – Research Coordinators use study visit checklists to ensure that all study required procedures and processes are met before, during and after the subject has been seen. Items listed on these checklists include informed consent obtained, consent questions answered (and by whom), vitals recorded, medications reviewed, etc. These checklists are reviewed by the study coordinator and are signed off for each study subject by the coordinator monitoring the study to ensure that protocols are followed accurately and include limited variance from protocol.
- Safety monitoring – The safety monitoring of subjects enrolled in the research includes both internal and external safety checks governing the administration of ¹⁸F-DCFPyL. Internal monitoring is performed by co-investigators and external monitoring by a team of four physicians with the appropriate broad clinical and technical. The internal monitoring plan includes a brief review of each subject visit after it occurs. In this regard, the study team will discuss data quality, ¹⁸F-DCFPyL production and administration, and subject compliance and tolerance of research procedures.

The external monitoring plan will be coordinated by the Department of Radiology Medical Imaging Research Support (MIRS) administrative team. MIRS is a working group that provides investigators with the support needed to conduct clinical research that uses imaging as an outcome measure. Members include a core administrative group (physicians, scientists, imaging modality managers, regulatory and administrative support) and ad hoc members recruited when their expertise is required for the review/monitoring of a research project. MIRS administrative team in addition to a 4-person committee of physicians/scientists will meet annually with representatives from the research team, to discuss research progress, AE/SAE reports, as well as other data reports compiled by the study team. If an AE/SAE occurs, an ad hoc committee meeting will be organized to discuss whether the event is considered serious, whether it can be attributed to research procedures, whether it constitutes non-compliance on the part of the study team, and the plan for resolution and a future remediation plan.

As part of this plan, the monitor(s) will verify that:

- The rights and well-being of human subjects are protected
- Reported study data are accurate, complete, and verifiable from source documents
- The conduct of the study is in compliance with the currently approved protocol, GCPs, applicable regulatory requirements, and guidelines for clinical research studies at the University of Wisconsin-Madison and its affiliates

